Hypothesis: The use of a novel adherence intervention (the AdhereTech bottle with reminders) will improve adherence to HIV medications over 12 weeks.

Primary Objective: To assess adherence to a tenofovir-based regimen over 12 weeks in patients using the AdhereTech bottle with reminders compared to the usual standard of care.

Primary Endpoint: The mean change in drug levels of tenofovir diphosphate (TFV-DP) in red blood cells using dried blood spots between week 0 and week 12 in the AdhereTech intervention group compared with the standard of care group.

Secondary Objectives:

- 1) To assess the feasibility of using the AdhereTech bottles with phone/text reminders in HIV-infected patients.
- 2) To assess the use of tenofovir diphosphate dried blood spots as a marker of HIV medication adherence in comparison with plasma tenofovir levels and self-reported medication adherence.

Secondary Endpoints:

- 1) The percentage of patients completing the 12 week AdhereTech intervention in comparison with the standard of care group.
- 2.1) Compare the mean change in TFV-DP blood spot level, TFV plasma level, and self-reported medication adherence between weeks 0 and 12 in the AdhereTech intervention and standard of care groups.
- 2.2) The mean change in HIV level and percent of patients with an HIV RNA below the level of detection between weeks 0 and 12 in the AdhereTech intervention and standard of care group.

RESEARCH PLAN:

Selection of Participants

Type of the Participant Population

This study is open to all adults who meet the following inclusion and exclusion criteria.

Inclusion and Exclusion Criteria:

Inclusion Criteria:

- Male and nonpregnant female subjects aged 18 years and older
- A diagnosis of HIV-1
- Undergoing therapy with a tenofovir-based antiretroviral regimen
- Suboptimal adherence to the tenofovir-containing HIV antiretroviral regimen over the prior 52 weeks from the time of enrollment, as evidenced by 2 HIV RNA levels above the level of

detection following an HIV RNA level below the level of detection, with no plans to change the current HIV drug regimen.

- Access to and willingness to use a cell phone to receive voice/text reminders to take HIV medications. Subjects must also agree to maintain a stable phone number and active cell phone service for the duration of the study.
- Adequate English to provide written, informed consent and to provide reliable responses to the study interview

Exclusion Criteria:

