regimen). During the initial visit, the study coordinators will program the AdhereTech bottle for a patient's preferred medication schedule and supply the patient with a toll-free number so they can further customize the bottles reminder features during the study.

The AdhereTech bottle will monitor the patient's adherence and wirelessly send this encrypted HIPAA compliant data to a central server. Based on the results, an automated phone call or text message will be generated to remind patients to take their medication from the AdhereTech bottle as scheduled. To protect patient privacy, the phone/text message will not disclose the patient's HIV status or the name of their HIV medication. In order to avoid accidental overdoing of HIV medications, the reminder will not specifically instruct the patient to take a dose of their medication at that time, but rather advise that s/he adhere to his/her normal dosing schedule. In the instance of a phone call, the patient will be able to leave feedback as to why they are missing their medication doses – this data will be recorded for subsequent analysis.

Before patients enroll in the study, we let them know that they are the true arbiter of when they need to take pills. Our device will remind them, but if they think there is an error then they should not take a pill. We will utilize a particular language to lessen the risk of medication errors. Our phone/text reminders will say "Please be sure to stay adherent to your medication dosing schedule". The reminder technology will never tell a patient that s/he missed a dose or instruct a patient to take a dose."

Patients in both groups will be required to come in for study visits every 4 weeks for a total of 4 visits over 12 weeks. At weeks 4, 8, and 12, all patients will undergo an interval history. At weeks 4 and 8, the study coordinators will refill the AdhereTech bottle for patients in the AdhereTech group.

At weeks 0, 4, 8, and 12, each subject will undergo a blood draw for a plasma tenofovir level and complete an adherence questionnaire via computer assisted self-interviewing (CASI). The adherence questionnaires will utilize forms QL0751, QL0752, and QL0742, developed by the Outcomes Committee of the AIDS Clinical Trials Group, sponsored by the NIH/NIAID, and are included in Appendices B-E.

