At weeks 0 and 12, patients will undergo testing for dried blood spot tenofovir diphosphate (TFV-DP) level, HIV RNA level, CD4 cell count, and safety labs (complete metabolic panel, phosphorous, liver function testing, and complete blood count). Please see tables 1 and 2 for the schedule of assessments and treatment plan.

All patients will receive reimbursement in the form of a Metro card, which will cover the cost of two subway rides (value \$5.50, in addition to the card purchasing fee). The cards will be provided at each visit, except for the initial screening visit.

Schedule of Events:

The schedule of study events is included below.

Table 1 – Schedule of Assessments

Visit Day and Window	Screening (Day - 45 to Day -1)	Enrollment (week 0, Day 0)	week 4 (+/- 7 days)	week 8 (+/- 7 days)	week 12 (+/- 7 days)
Obtain informed consent	X				
Randomization		X			
History and physical exam	X				
AdhereTech bottle filled and dispensed		X	X	X	
Interval history		X	X	X	X
Routine adherence counseling		X			
Dried blood spot for TFV-DP level		X			X
Plasma for TFV level		X	X*	X*	X
Plasma HIV RNA level		X			X
Whole blood CD4 cell count		X			X
Plasma BMP, LFTs, and phosphorous		X			X
Adherence questionnaire by CASI		X	X	X	X

Abbreviations: *TFV-DP – tenofovir diphosphate, TFV – tenofovir, BMP – basic metabolic panel, LFTs – liver function tests*

*For the secondary analysis, plasma TFV levels will be analyzed from weeks 0 and 12. If additional funding is obtained, we will analyze replicate specimens at weeks 0 and 12 plus weeks 4 and 8.

Table 2 – Blood volumes

Bodily Fluid	Amount	Frequency	Total
Blood - Plasma TFV	6mL	Weeks 0, 4, 8, and 12	36ml
Blood – TFV-DP blood spot *	4mL	Weeks 0 and 12	12mL
Blood – HIV RNA	6 ml	Weeks 0 and 12	12mL
Blood – CBC and CD4 cell count	6mL	Week 0	6mL
Blood – BMP, phosphorous, LFTs	6ml	Weeks 0 and 12	12mL

Abbreviations: *TFV-DP – tenofovir diphosphate, TFV – tenofovir, CBC – complete blood count, BMP – basic metabolic panel, LFTs – liver function tests*

*All labs will be processed locally at Weill Cornell/NYPH. The TFV-DP dried blood spot and plasma TFV levels will be assayed by the Colorado Antiviral Pharmacology Laboratory at the University of Colorado Denver. Protocol is included in Appendix F.

HIV Therapy:

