In this pilot study, the sample size calculation is based on the null hypothesis of no difference in tenofovir-diphosphate (TFV-DP) concentrations (by dried blood spots) at baseline versus a demonstrable difference at week 12. From a simulation study (Castillo), we expect to see the same mean concentration (standard deviation) at both groups at baseline: 900 (404) fmol/punch. At 12 weeks, we expect to see a mean concentration (standard deviation) of 1332 (597) fmol/punch in arm A (adherence intervention) vs. 900 (404) fmol/punch in arm B (control). Assuming normal distribution of TFV-DP concentrations, type 1 error = 0.05, power = 80%, a sample size of 32 will be recruited per arm (64 total) based on a two-sided, two-sample t-test with equal variance. Since the data may have missing data at the last visit, we will add ~10% more participants. Therefore, the final sample size of 35 per arm (70 total) will be enrolled.

We intend to screen approximately 100 total subjects, as we assume there will be subjects who may sign the consent form, but ultimately do not participate in the study due to screen failure, not meeting inclusion/exclusion criteria, and personal choice.

Randomization will be provided by the biostatistician from Weill Cornell Medical College. The randomization list will be provided to the principal investigators.

Data Analysis:

For the primary analysis, we will compare the mean change in drug levels of tenofovir diphosphate (TFV-DP) in red blood cells using dried blood spots between week 0 and week 12 in the AdhereTech intervention group compared with the standard of care group via a two-sided t-test. If the data will not meet the normal assumption, non-parametric Wilcoxon Rank Sum test will be used to test medians between two groups.

For the secondary analyses, we will:

- Calculate the mean percentage of patients who complete the 12 week AdhereTech intervention and compare that with the percent that complete 12 weeks of follow-up in the standard of care group.
- Compare the mean change in TFV-DP blood spot level with TFV plasma level and self-reported medication adherence from weeks 0 and 12 between the AdhereTech intervention and standard of care groups.
- Compare the mean change in HIV level and median percent of patients with an HIV RNA below the level of detection from weeks 0 and 12 between the AdhereTech intervention and standard of care group.

These analyses will be performed via two-sided t-tests.

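### Self-reported adherence is collected at weeks 0, 4, 8 and 12 but compared only as a week 0 to 12 change, so two post-baseline visits go unused and patients without a week-12 report drop out of the comparison

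*Combined protocol and SAP*

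**What the plan says.** - **Collection.** The Study Visits section states: "At weeks 0, 4, 8, and 12, each subject will undergo a blood draw for a plasma tenofovir level and complete an adherence questionnaire". In Table 1 the row "Adherence questionnaire by CASI" is marked at all four visits, with no asterisk.
- **Funding condition.** The Table 1 footnote, "If additional funding is obtained, we will analyze replicate specimens at weeks 0 and 12 plus weeks 4 and 8", concerns plasma tenofovir specimens, not the questionnaire.
- **Endpoint.** Secondary Endpoint 2.1 takes the mean change in "self-reported medication adherence between weeks 0 and 12 in the AdhereTech intervention and standard of care groups", alongside the changes in TFV-DP and plasma tenofovir.
- **Analysis.** Data Analysis repeats the two-visit comparison, "self-reported medication adherence from weeks 0 and 12 between the AdhereTech intervention and standard of care groups", and adds: "These analyses will be performed via two-sided t-tests".
- **Missing data.** The Sample Size Estimate says "Since the data may have missing data at the last visit, we will add ~10% more participants". Data Analysis puts an intention-to-treat analysis first. Discontinuing a Patient keeps discontinued patients in the study for that analysis. No imputation or likelihood-based method is given.
- **Early withdrawal.** Patients who withdraw are encouraged to attend a visit that includes a questionnaire. No rule says how that questionnaire enters the analysis.

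**The concern.** Patients supply three post-baseline reports of adherence and the plan uses one. The other two need no assay and no further funding.

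A t-test on the week 0 to 12 change needs both values. A patient who leaves after week 8 has a baseline and two follow-up reports but adds nothing to the arm comparison, although the analysis is described as intention-to-treat. Enrolling more patients restores numbers but does not deal with selective loss. The reasons for discontinuation that the protocol lists, such as hospital admission, incarceration, severe illness or refusal of blood draws, could plausibly be related to adherence.

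At stake are the precision of the self-report comparison and its exposure to dropout, and, through secondary objective 2, the use of self-report as a comparator for TFV-DP.

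**Working it through.** **The plan's own figure.** The documents give no sample size or effect size for self-report. The only figure is 32 per arm for TFV-DP. With a difference of 1332 − 900 = 432 and SD 597 in both arms, n = 2 × (1.960 + 0.842)² × 597² / 432² = 30 per arm by the normal formula and 31 by the t distribution, against 32 stated. It therefore reproduces within 2 patients. This point does not depend on it, except that 32 and 35 per arm serve below as completers and enrolled.

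**Counts.**
- Scheduled post-baseline questionnaires: 3 × 70 = 210.
- Used by the plan: at most 70.
- Unused: 140, or two thirds.
- Without a week-12 change score at the plan's allowance: 70 − 64 = 6 patients, 3 per arm.

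**Assumptions not in the documents.** Equal variance at each visit (set to 1), and either a common correlation r between visits (compound symmetry) or r between adjacent visits that decays with time (AR(1)). The 3 patients per arm who miss week 12 have weeks 0, 4 and 8.

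**Variance of the week-12 arm difference.** Let ρ be the week 0 to 12 correlation, which is r under compound symmetry and r³ under AR(1).
- Planned change-score t-test in completers: 2 × 2(1 − ρ)/32.
- Week-12 ANCOVA in completers: 2(1 − ρ²)/32.
- Repeated-measures model in all 70 patients with a common baseline mean: generalised least squares, computed numerically.

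| Structure | r | Change t-test | ANCOVA | Repeated measures | Ratio to t-test | Ratio to ANCOVA |
|---|---|---|---|---|---|---|
| Compound symmetry | 0.3 | 0.0875 | 0.0569 | 0.0565 | 0.645 | 0.993 |
| Compound symmetry | 0.5 | 0.0625 | 0.0469 | 0.0462 | 0.739 | 0.986 |
| Compound symmetry | 0.7 | 0.0375 | 0.0319 | 0.0312 | 0.832 | 0.979 |
| Compound symmetry | 0.8 | 0.0250 | 0.0225 | 0.0220 | 0.879 | 0.977 |
| AR(1) | 0.3 | 0.1216 | 0.0625 | 0.0620 | 0.510 | 0.992 |
| AR(1) | 0.5 | 0.1094 | 0.0615 | 0.0603 | 0.551 | 0.980 |
| AR(1) | 0.7 | 0.0821 | 0.0551 | 0.0532 | 0.647 | 0.964 |
| AR(1) | 0.8 | 0.0610 | 0.0461 | 0.0441 | 0.723 | 0.956 |

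The ratio of ANCOVA to the change-score test is (1 + ρ)/2, so baseline adjustment alone gives most of the gain. The last column isolates what weeks 4 and 8 add: about 1 to 4%.

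**If the target were the average over weeks 4, 8 and 12.**
- Compound symmetry: the variance of the change is (1 + 2r)/3 + 1 − 2r = (4/3)(1 − r), against 2(1 − r) for week 12. The ratio is 0.667 at any r, and the SE ratio is 0.816.
- AR(1) at 0.7: 0.731 against 1.314, a ratio of 0.557 and an SE ratio of 0.746.
- The average therefore gains power only if its effect exceeds about 82% of the week-12 effect under compound symmetry, or about 75% under AR(1) at 0.7.
- If the effect builds linearly (1/3, 2/3, 1), the average effect is 2/3 of the week-12 effect. Where the week-12 comparison has 80% power, the average has Φ(2.80 × 0.667/0.816 − 1.96), about 63%, under compound symmetry. Under AR(1) at 0.7 it has about 71%.

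**The case against.** **Week 12 is a coherent target.** TFV-DP is measured only at weeks 0 and 12, and plasma tenofovir is analysed only at those visits unless further funding arrives. Secondary objective 2 compares these markers, so using the same two visits for all three is reasonable. This stands, and it is why the week-12 contrast should remain the main one.

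**A large gain might be inferred.** A reader might conclude that averaging weeks 4 to 12 cuts the variance by one third, equivalent to 50% more patients (1/0.667 = 1.5). That describes a different estimand from endpoint 2.1, and lower variance is not higher power if the effect builds over time. The documents give no time course. A reader might also argue that the trial's aim of better adherence over 12 weeks calls for the average. That wording belongs to the hypothesis and the primary objective, whose endpoint is TFV-DP. Secondary objective 2 does not contain it.

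**A stated exclusion might be inferred.** The plan nowhere says that patients who miss week 12 are excluded. The loss follows from a change-score t-test with no missing-data method. Some withdrawing patients will also have an exit questionnaire. The gap is the missing rule for using it.

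**Limits that more visits do not remove.** Self-report in an open-label trial is open to reporting bias. The recall period and scoring are in appendices not available for this review, so it cannot be judged how much time one report covers or how well a normal-theory model fits the score. The planned t-test also rests on a normal-theory comparison of means.

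**Conclusion.** The concern holds as a cheap improvement to one secondary analysis. The week 4 and 8 questionnaires are collected and not analysed. About 6 of 70 patients would contribute nothing to the self-report comparison at the plan's allowance, despite the intention-to-treat label. With week 12 kept as the target, a baseline-adjusted repeated-measures model has a variance of 0.65 to 0.88 (compound symmetry) or 0.51 to 0.72 (AR(1)) of the planned test.

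These ranges rest on assumed correlations of 0.3 to 0.8, equal variances, and patients who miss week 12 having their earlier reports. A patient with no post-baseline report adds essentially nothing to the arm difference under either method. The interim visits contribute little precision themselves. Their value is in retaining patients and in making missing-at-random more plausible. Neither the primary TFV-DP endpoint nor the trial's main conclusion is touched.

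**What to change.** Before self-report is compared by arm, amend Data Analysis as follows:

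1. Analyse self-reported adherence with a repeated-measures model of weeks 4, 8 and 12, with week-0 score, arm, visit and arm-by-visit, in all randomised patients with at least one post-baseline questionnaire.
2. Name the week-12 arm difference as the main contrast, to match endpoint 2.1 and the two-visit drug-level measures.
3. Assign an early-withdrawal questionnaire to its nearest scheduled visit.
4. Report the average arm difference over weeks 4 to 12 as supportive only.

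The cost is a paragraph of text and a few lines of code, with no new data. The downside is slightly more analysis work and reliance on a missing-at-random assumption, which should be stated.

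### The secondary HIV RNA analysis is a t-test on change in level with no scale, below-limit rule or fallback stated, and suppression is summarised by an unusable median percent

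*Combined protocol and SAP*

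**What the plan says.** The Data Analysis section lists three secondary analyses: completion of 12 weeks, change in the adherence markers, and HIV RNA. The HIV RNA item reads "Compare the mean change in HIV level and median percent of patients with an HIV RNA below the level of detection"; the completion item begins "Calculate the mean percentage of patients who complete the 12 week AdhereTech intervention". One sentence then covers all three: "These analyses will be performed via two-sided t-tests".

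Secondary Endpoint 2.2 defines the same virologic endpoint as "The mean change in HIV level and percent of patients with an HIV RNA below the level of detection between weeks 0 and 12", without the word *median*.

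A fallback for non-normal data appears once, in the paragraph on the primary analysis: "If the data will not meet the normal assumption, non-parametric Wilcoxon Rank Sum test will be used to test medians between two groups". It is not repeated or cross-referenced for the secondary analyses. The document nowhere names a scale for HIV RNA, a value to use for results below the detection limit, a test for categorical data, or a confidence interval for a difference in proportions.

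**The concern.** HIV RNA commonly spans orders of magnitude and is cut off below at the detection limit. This population should show both features. Entry requires suboptimal adherence "as evidenced by 2 HIV RNA levels above the level of" detection after an earlier undetectable result, so values will run from the limit upward. On copies/mL, the mean change in an arm is then set largely by a few patients with high values, and a real fall in most patients can be lost.

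Endpoint 2.2 is the only listed endpoint that measures virologic benefit. The trial is open-label, so a scale left open until the data are seen is a choice that could decide this result.

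Separately, a *median percent of patients* has no workable meaning. Each arm has one percentage, and the median of a yes/no outcome coded 0/1 is 0, 1 or, on a tie, 0.5.

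**Working it through.** **Sample size used.** The plan gives no power for the secondary endpoints. Its 32 per arm is for TFV-DP and is reproduced closely with the larger SD: 2 × (1.960 + 0.842)² × (597/432)² = 2 × 7.85 × 1.91 ≈ 30 per arm. The t-distribution version gives 31, and 32 per arm gives 81.3% power. The checks below use 32 or 35 per arm.

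**HIV RNA: inputs, all assumed.** Log10 mean 3.5 at baseline, SD 0.7 or 1.0, correlation between weeks 0 and 12 of 0.3 or 0.5, limit 20 copies/mL with lower values set at 20, true fall 0.75 log10 in one arm and none in the other, 32 per arm, two-sided 5%.

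**Log10 scale, by formula (ignoring the limit).** SD of change = SD × √(2(1 − ρ)). Non-centrality = 0.75 / SD of change × √(32/2). Power ≈ Φ(non-centrality − 2.00).

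| SD | ρ | SD of change | Non-centrality | Formula power, log10 | Simulated, log10 | Simulated, raw copies |
|---|---|---|---|---|---|---|
| 0.7 | 0.3 | 0.828 | 3.62 | 0.95 | 0.94–0.95 | 0.24–0.25 |
| 0.7 | 0.5 | 0.700 | 4.29 | 0.99 | 0.99 | 0.29 |
| 1.0 | 0.3 | 1.183 | 2.54 | 0.70 | 0.69–0.70 | 0.08–0.09 |
| 1.0 | 0.5 | 1.000 | 3.00 | 0.84 | 0.82–0.83 | 0.09–0.10 |

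The simulations used 20,000 trials per row and apply the limit; repeat runs differ by about one percentage point. The raw mean difference pointed the wrong way in about 10–24% of trials.

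**Why the raw scale fails.** For a log-normal variable the coefficient of variation is √(exp((2.303 × SD)²) − 1). That is √(13.4 − 1) ≈ 3.5 at SD 0.7 and √(200.7 − 1) ≈ 14 at SD 1.0. The scatter swamps a difference in means at 32 per arm.

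**A second set of assumptions.** Median 1000 copies/mL, limit 20, correlation 0.6, newly suppressed 20% v 60%, log10 SD 0.6–1.2, 35 per arm, 3,000 trials each. Power was 2–14% raw against 60–83% on log10. Under no effect, the raw test rejected in 1.3–3.4% of trials, so the harm is lost power and not false positives. A Wilcoxon test on raw change reached 25–35%, so extending the fallback would recover only part of the loss.

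**Median percent.** Read literally, any two arms that are both less than half suppressed share a median of 0. For example, 45% v 20% would appear as 0 v 0. By contrast, the *mean percentage* wording for completion is harmless, because the mean of a 0/1 variable is the proportion.

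**t-test on yes/no endpoints.** All tables were enumerated: 36² = 1296 at 35 per arm and 33² = 1089 at 32 per arm. In four tables of each set neither arm varies (for instance, everyone in both arms completes) and the t-test is undefined. In the remaining 1292 and 1085 tables, the pooled t-test and the uncorrected Pearson chi-square make the same 5% decision every time. Maximum type I error is 0.057 at 35 per arm and 0.060 at 32 per arm.

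**The case against.** Two stronger readings are tempting, and neither is supported.

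*The plan prescribes an untransformed analysis.* A reader might infer this from the words *HIV level*. The text is silent: it names neither copies/mL nor log10, and an analyst may well choose log10. The power loss above is therefore the cost of one permitted reading, not of a stated instruction. What stands is that the scale and the below-limit rule are unspecified.

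*The t-test makes the completion and suppression results wrong.* A reader might infer this because the outcomes are binary, or from a borderline table. For 35/35 v 31/35 the t-test gives p = 0.040 and Fisher 0.114. But chi-square gives 0.039 and Barnard's unconditional exact test 0.042, while Boschloo with the arms as fixed margins gives 0.072. The exact tests disagree among themselves, so this table does not convict the t-test. Nor is Fisher a free improvement: its maximum size at 35 per arm is 0.029, and for an assumed 30% v 60% its power is 0.62 against 0.71 for the t-test and chi-square.

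It is also fair to say that *median percent* is probably a slip, since endpoint 2.2 says percent; that these are secondary endpoints of a 70-patient pilot with no power claimed for them; and that every HIV RNA input above is assumed. This limits the weight of the point. It does not remove the need to reconcile the two texts and fix the scale before analysis.

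**Conclusion.** The point holds as a gap in specification with one error of wording. The HIV RNA analysis lacks a scale, a below-limit rule and a fallback. If it is run on copies/mL, power for a 0.75 log10 fall is about 9–29%, against about 70–99% on log10 change, given the assumed distribution. The second scenario gives the same ordering, so the direction does not hang on one set of values, but the exact figures do. The *median percent* summary is unusable and conflicts with endpoint 2.2. For the yes/no endpoints, the remaining defects are that no categorical method or interval is named and that the t-test is undefined when neither arm varies; no inflation of false positives is claimed. The primary TFV-DP comparison is untouched.

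**What to change.** 1. State that HIV RNA is analysed as log10 copies/mL, with values below the detection limit set at the limit. Compare week-12 log10 HIV RNA between arms with baseline log10 HIV RNA as covariate. With equal variances, adjustment cuts the SD relative to change by a factor √((1 + ρ)/2): 0.81 at ρ = 0.3 and 0.87 at ρ = 0.5. This is a gain in efficiency; naming the scale is the essential repair.
2. Delete *median* from the suppression item so that the Data Analysis section matches endpoint 2.2.
3. Report suppression and completion as n (%) per arm, with the difference in proportions, a score-type 95% CI, and a chi-square or unconditional exact test. Restrict the t-test sentence to continuous endpoints.

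The cost is SAP wording and minor analysis work. No assessment is added, because the schedule already provides it: "At weeks 0 and 12, patients will undergo testing for dried blood spot tenofovir diphosphate (TFV-DP) level, HIV RNA level".
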